#### Lesions with Prior Local Treatment:

- Tumour lesions situated in a previously irradiated area or in an area subjected to other loco-regional therapy are usually not considered measurable unless there has been demonstrated progression in the lesion.

### **METHODS FOR ASSESSING LESIONS**

All measurements should be recorded in metric notation, using calipers if clinically assessed. All baseline evaluations should be performed as close as possible to the treatment start and never more than 4 weeks before the beginning of the treatment.

The same method of assessment and the same technique should be used to characterize each identified and reported lesion at baseline and during the study.

Imaging-based evaluation should always be the preferred option.

### **CLINICAL LESIONS**

Clinical lesions will only be considered measurable when they are superficial and  $\geq 10$  mm in diameter as assessed using calipers (e.g., skin nodules). For the case of skin lesions, documentation by colour photography, including a ruler to estimate the size of the lesion, is suggested.

### **CHEST X-RAY**

Chest CT is preferred over chest X-ray, particularly when progression is an important endpoint, since CT is more sensitive than X-ray, particularly in identifying new lesions.

However, lesions on chest X-ray may be considered measurable if they are clearly defined and surrounded by aerated lung.

### **CT AND MRI SCANS**

CT is the best currently available and reproducible method to measure lesions selected for response assessment. In this guideline, the definition of measurability of lesions on CT scan is based on the assumption that CT slice thickness is  $\leq 5$  mm. When CT scans have slice thickness of  $> 5$  mm, the minimum size for a measurable lesion should be twice the slice thickness. MRI is also acceptable.

If prior to enrolment it is known that a patient is unable to undergo CT scans with intravenous (IV) contrast because of allergy or renal insufficiency, the decision as to whether a non-contrast CT or MRI (without IV contrast) will be used to evaluate the patient at baseline and during the study should be guided by the tumour type under investigation and the anatomic location of the disease. For patients who develop contraindications to contrast after baseline contrast CT is done, the decision as to whether non-contrast CT or MRI (enhanced or non-enhanced) will be performed should also be based on the tumour type and the anatomic location of the disease, and should be optimized to allow for comparison with the prior studies if possible. Each case should be discussed with the radiologist to determine if substitution of these other approaches is possible and, if not, the patient should be considered not evaluable from that point forward. Care must be taken in measurement of target lesions and interpretation of non-target disease or new lesions on a different modality, since the same lesion may appear to have a different size using a new modality.

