#### *11.4.3.4 Secondary Efficacy Endpoint Analyses*

The ORR according to Investigator's assessment (cohort A and cohort B) and by independent central review (cohort B) will be presented with their associated 2-sided 95% CIs using Clopper-Pearson exact method. Discordance in ORR assessed by independent central review and by Investigator will be described.

DCR estimates will be presented in statistical tables with associated 2-sided 95% CIs.

Time-to-event endpoints (TTR, DOR, PFS and OS) will be analysed using the Kaplan-Meier method. The results will be presented for each Cohort A and B both in summary tables and graphically in Kaplan-Meier plots. Kaplan-Meier methodology will be used to characterise the

distribution of endpoints. Median durations and associated 2-sided 95% CIs will be provided. Event rates at timepoints from either first dose of study treatment or first documented response will also be estimated with associated 2-sided 95% CIs.

General censoring rules for the analysis of PFS are described below:

- Subjects who receive non-protocol anti-cancer therapy (NPACT) after start of cabozantinib and before experiencing an event will be right censored at the date of the last tumour assessment prior to the date of initiation of subsequent therapy;
- Subjects who have not experienced an event (and are not otherwise censored) at the time of data cut-off will be right censored on the date of their last tumour assessment;
- Subjects who miss two or more scheduled tumour assessments followed by an event will be right censored on the date of their most-recent tumour assessment prior to the missing assessments.

Additional supportive analyses of PFS will be defined in the SAP using alternative event definitions and censoring schemes to account for partial or completely missing assessments, address bias due to tumour assessment timing, evaluate the impact of potentially informative censoring, and to address potential discrepancies between the documentation of progression per the Investigator and per the independent central review.

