## **MISSING ASSESSMENTS AND NOT-EVALUABLE DESIGNATION**

When no imaging/measurement is done at all at a particular timepoint, the patient is not evaluable at that timepoint. If measurements are made on only a subset of target lesions at a timepoint, usually the case is also considered not evaluable at that timepoint, unless a convincing argument can be made that the contribution of the individual missing lesions would not change the assigned timepoint response. This would be most likely to happen in the case of PD. For example, if a patient had a baseline sum of 50 mm with three measured lesions and during the study only two lesions were assessed, but those gave a sum of 80 mm, the patient will have achieved PD status, regardless of the contribution of the missing lesion.

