Concordance in Overall Response Rate and BOR assessed by independent central review and by Investigator will be described using shift tables for each cohort separately (Tables 14.2.4.3 and 14.2.4.4). The concordance will be presented for the subjects with assessments in both populations i.e. from both IRC and investigator assessments.

General censoring rules for the analysis of PFS are described in [Appendix 1 \(4\)](#).

Additional supportive analyses of PFS below will be performed using alternative event definitions and censoring schemes to account for partial or completely missing assessments, address bias due to tumour assessment timing, evaluate the impact of potentially informative censoring, and to address potential discrepancies between the

SAP Final: Version 6.0: 17 August 2023

documentation of progression per the Investigator and per the independent central review. This is applicable for PFS only. These additional supportive analyses will be performed on the Efficacy population only.

- The primary PFS analyses described above will be repeated with the same general censoring rules, except that the progression or death will be considered a PFS event regardless of when it occurs during the study i.e. the event will be considered a PFS event even if the subjects missed two or more scheduled tumour assessment prior this event and/or even if the subjects received NPACT prior the event (Table 14.2.2.4, Figure 14.2.2.5, Table 14.2.5.5 and Figure 14.2.5.6);
- The primary PFS analyses described above will be repeated with the same general censoring rules, except that non-radiological disease progression will also be considered a PFS event (Table 14.2.2.6, Figure 14.2.2.7, Table 14.2.5.7 and Figure 14.2.5.8).
- The primary PFS analyses described above will be repeated with the same general censoring rules, with additional censoring at last tumour assessment prior to treatment discontinuation for subjects who discontinued study treatment due to reasons other than PD or death (Table 14.2.2.8, Figure 14.2.2.9, Table 14.2.5.9 and Figure 14.2.5.10).

3.2.2 *Safety*

All safety data will be included in the subject data listings. Analyses and summary tables will be based upon the safety population as defined in Section 2.2 and will be presented in each cohort separately and overall.

3.2.2.1 *Adverse events*

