In case of non-censoring and a partial progression/death date, missing day will be imputed by the first day of the month. This will be the most conservative approach considering that the earliest date for progression/date. It will be imputed by the date of initial response in case the date of initial response is later than the imputed date.

In case of censoring and a partial last tumour assessment date, missing day will be imputed by the first day of the month. It will be imputed by the date of initial response in case the initial response is later than the imputed date. The censoring may occur earlier than the exact date.

(4) Time-to-Progression for Progression-Free Survival (PFS) analysis

PFS is defined as the time from start of study treatment to either disease progression (as determined by independent central review per RECIST 1.1) or death due to any cause, whichever occurs first. For subjects who are not known to have died or progressed at the time of data cut-off for PFS analysis, the PFS will be censored at the last tumour assessment and considering the censoring rules defined in the table below.

| Event | Decision | Date of event or censoring |
|---|--------------|---|
| Progressive disease with no more than one missing scheduled tumor assessment before the event and without NPACT before the event. | Not censored | Date of first progressive disease |
| Death with no more than one missing scheduled tumor assessment before the event and without NPACT before the event. | Not censored | Date of death |
| PD or death with two or more missing scheduled tumor assessments before the event | Censored | Date of the last tumor assessment prior to the missing assessment. |
| PD or death with NPACT after the start of cabozantinib and before the event | Censored | Date of the last tumor assessment prior to the date of initiation of NPACT. |
| No event (no PD, no death) with at least one radiological | Censored | Date of last radiological assessment |

SAP Final: Version 6.0: 17 August 2023

| | | |
|---|----------|-----------------------------------|
| assessment after the initiation of study treatment. | | |
| No event (no PD, no death) without any radiological assessment after the initiation of study treatment. | Censored | Date of first cabozantinib intake |

PFS will be calculated as:

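### PFS and DOR are censored at the last scan without requiring it to be evaluable, so trailing not-evaluable scans are credited as progression-free time

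*Protocol*

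**What the plan says.** Protocol Appendix 5 produces NE timepoints in three ways:

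- No scan: "When no imaging/measurement is done at all at a particular timepoint, the patient is not evaluable at that timepoint".
- A scan with incomplete measurement: "If measurements are made on only a subset of target lesions at a timepoint, usually the case is also considered not evaluable at that timepoint". Table A5.1 has a matching row.
- Contrast becomes contraindicated after baseline and neither non-contrast CT nor MRI can replace it: "the patient should be considered not evaluable from that point forward".

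In the second and third cases a scan can be on file.

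The censoring text does not mention evaluability. Under Protocol 11.4.3.4, subjects without a PFS event "will be right censored on the date of their last tumour assessment". In SAP Appendix 1 (3) for DOR and (4) for PFS, the table row for event-free subjects with a post-treatment or post-response scan gives "Date of last radiological assessment". The fallback to first dose or first response applies only when there was no radiological assessment at all.

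The rule on gaps is triggered by missed scans: "Subjects who miss two or more scheduled tumour assessments followed by an event will be right censored" in the protocol, and in the SAP tables "PD or death with two or more missing scheduled tumor assessments before the event". The SAP's handling of missing tumour data in Appendix 1 (1) is written for best overall response. SAP 3.2.1.2 says the supportive PFS analyses are there, among other aims, "to account for partial or completely missing assessments".

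**The concern.** A censoring date states that the subject was followed and known to be event-free up to that day. A scan on which the target lesions could not all be assessed cannot support that statement for target-lesion progression. If such a scan sets the date, the subject stays in the Kaplan-Meier risk set over an interval in which target-lesion progression could not be detected, and the curve is lifted.

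The case that matters most is a subject who becomes permanently NE but continues to be scanned. SAP 1.3.2.1 keeps scans going every 12 weeks, and for subjects off treatment until the Investigator confirms radiographic progression, so such a subject can accumulate scan dates with no evaluable result. The situation is not far-fetched: Appendix 5 names renal insufficiency as a reason for being unable to have contrast, and SAP 3.2.2.1 lists renal failure as an event of special interest. At stake are the estimates for PFS and DOR, by central review and by Investigator.

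**Working it through.** **Design figure.** The plan gives no sample size, event count or power for PFS or DOR. Its one design figure is for ORR. With 68 subjects, null 10% and alternative 23%, the exact one-sided test at 0.025 rejects at 13 or more responders, with attained alpha 0.0163 and power 81.6%. Inflation gives 68/0.93 = 73.1, rounded up to 74. The stated 80% and 74 are reproduced, and no censoring rule enters them.

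**Inputs for the censoring check.** Scans are every 12 weeks, or 84 days (SAP 1.3.2.1), with target Days 85, 169 and 253 (SAP 3.2.12). Time in months = (date − start date + 1)/30.4375, where the start is first dose for PFS and first response for DOR (SAP Appendix 1 (3)-(4)).

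**Individual subjects.**

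- Credit per trailing NE scan: 84/30.4375 = 2.76 months.
- PFS, stable disease at Week 12, NE at Weeks 24 and 36, no event. As written: 253/30.4375 = 8.31 months. At the last evaluable scan: 85/30.4375 = 2.79 months. Credited without evidence: 168/30.4375 = 5.52 months.
- PFS, only post-baseline scan (Day 85) is NE. As written: 2.79 months. With no evaluable scan, censoring would be at Day 1.
- DOR, response at Week 12, NE at Weeks 24 and 36, no event. As written: (253 − 85 + 1)/30.4375 = 5.55 months. With no evaluable scan after response, censoring would be at the date of first response.

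**Cohort level (illustrative simulation; NE shares are assumed).** Setting 1: 68 subjects, exponential PFS with true median 8 months, 12-39 months of follow-up, 3% drop-out per month, 600 replicates. Setting 2: 74 subjects, true median 7.4 months (the METEOR cabozantinib figure in Protocol 1.2.1.1), 12-30 months of follow-up, 300 replicates. Both use 12-week scans.

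| Setting | Permanently NE, still scanned | 12-month PFS as written | At last evaluable scan | Difference (points) | Median, months (as written vs last evaluable) |
|---|---|---|---|---|---|
| 1 | 5% | 39.6% | 38.2% | 1.4 | 9.75 vs 9.55 |
| 1 | 10% | 41.0% | 38.3% | 2.7 | 10.05 vs 9.55 |
| 2 | 5% | 37.5% | 35.3% | 2.2 | 8.96 vs 8.78 |
| 2 | 10% | 39.7% | 35.4% | 4.3 | 9.38 vs 8.87 |

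Setting 2 scans permanently NE subjects to cut-off and lets them have no further event of any kind, so it leans to the high side for a given NE share.

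- Sporadic NE: with 10% of scans NE at random (setting 1), 6-month PFS is 64.1% as written and 63.5% at the last evaluable scan, a difference of 0.6 points.
- Two consecutive NE scans, then evaluable again, in 10% of subjects (setting 2): 12-month PFS is 36.1% as written. It is 36.8% if the censoring date is changed and NE scans are also counted as missed. The direction reverses because later progressions that were events become censored.

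**DOR.** Expected responders: 0.23 × 68 = 15.6, about 16, so one affected responder is 1/16, or about 6% of the DOR sample.

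**The case against.** The strongest reply is that this is an unqualified term, not an instruction. No text directs censoring at an NE scan, and a careful programmer might already use the last evaluable one. That is fair as a description. But the tables name a date, an NE scan satisfies the name, and two programmers could derive different PFS from the same data.

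A second reply is scale. The shift needs permanent NE with continued scanning. Exclusion criterion 4 removes subjects with a contrast or MRI contraindication at entry, and if scanning stops when the subject becomes permanently NE, the last scan is the last evaluable one and no bias arises. Sampling error is also much larger: 1.96 × √(0.39 × 0.61/68) is about 12 points, ignoring censoring. This stands and limits the weight of the point. A third reply is that the IRC charter may define NE for central review. It was not available, but censoring dates are set in the SAP.

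A reader might go further and infer that an NE scan leaves tumour status as unknown as a missed scan, so that two NE scans should trigger the two-missed rule. The documents do not support this. In Table A5.1 the NE row requires non-target disease without progression and no new lesion, and Appendix 5 still allows progression to be called when the measured subset suffices. A missed scan excludes nothing. Counting NE as missed would also censor deaths and new-lesion progressions that follow two NE scans. A reader might likewise infer that the supportive PFS analyses leave the whole matter untouched. The first of them already counts progression or death as an event regardless of missed scans, so progression after missed and after NE scans is treated alike there. What none of the three does is make the censoring date depend on evaluability, so the stated aim of covering partial assessments is not met for event-free subjects.

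**Conclusion.** The point holds for the censoring date. As written, PFS and DOR credit 2.76 months per trailing NE scan to event-free subjects, and the bias is upward. It is negligible for sporadic NE. It is 1.4 to 4.3 points in 12-month PFS, and about 0.2 to 0.5 months in the median, if 5-10% of subjects become permanently NE and are still scanned. Those shares are assumptions; the documents give none. For DOR, with about 16 expected responders, a single affected subject is noticeable.

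PFS and DOR are secondary endpoints without a planned hypothesis test, so the ORR test, its alpha, power and sample size do not change. The claim does not extend to the two-or-more-missed rule, where treating NE as missed is a debatable trade-off that moves the estimate the other way.

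A smaller wording conflict remains in Appendix 5. Making a patient NE from a point onward does not fit Table A5.1, where a new lesion or non-target progression gives PD whatever the target-lesion status.

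**What to change.** - In SAP Appendix 1 (3) and (4), define the censoring date as the last evaluable tumour assessment, meaning an overall timepoint response other than NE. If there is none, use the date of first response for DOR and of first dose for PFS. Align Protocol 11.4.3.4 and the DOR estimand text (Protocol 11.4.3.2, SAP 3.1.2).
- Keep observed progression and death after NE scans as events in the main analysis. Counting NE scans as missed in the two-or-more-missed rule should be at most a sensitivity analysis, labelled as such.
- In Appendix 5, reconcile the sentence on permanent non-evaluability with Table A5.1, for example by limiting it to target-lesion response.

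The cost is a few lines of text and one programming condition on response data already collected. Reported PFS and DOR may be slightly less favourable.

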#### **ENDOSCOPY, LAPAROSCOPY, ULTRASOUND, TUMOUR MARKERS, CYTOLOGY, HISTOLOGY**

Endoscopy, laparoscopy, ultrasound, tumour markers, cytology, and histology cannot be used for objective tumour evaluation.

#### **ASSESSMENT OF TUMOUR BURDEN**

To assess objective response or future progression, it is necessary to estimate the overall tumour burden at baseline and use this as a comparator for subsequent measurements.

#### **IDENTIFICATION OF TARGET AND NON-TARGET LESIONS**

When more than one measurable lesion is present at baseline, all lesions up to a maximum of five lesions total (and a maximum of two lesions per organ) representative of all involved organs should be identified as target lesions and will be recorded and measured at baseline. This means that, for instances in which patients have only one or two organ sites involved, a maximum of two lesions (one site) and four lesions (two sites), respectively, will be recorded. Other lesions (albeit measurable) in those organs will be considered non-target lesions.

Target lesions should be selected on the basis of their size (lesions with the longest diameter) and should be representative of all involved organs, but in addition should lend themselves to reproducible repeated measurements. It may be the case that, on occasion, the largest lesion does not lend itself to reproducible measurement, in which circumstance the next largest lesion that can be measured reproducibly should be selected.

Lymph nodes merit special mention since they are normal anatomical structures that may be visible by imaging even if not involved by tumour. As noted above, pathological nodes that are defined as measurable and may be identified as target lesions must meet the criterion of a short axis of  $\geq 15$  mm by CT scan. Only the short axis of these nodes will contribute to the baseline sum. The short axis of the node is the diameter normally used by radiologists to judge if a node is involved by solid tumour. Lymph node size is normally reported as two dimensions in the plane in which the image is obtained (for CT, this is almost always the axial plane; for MRI, the plane of acquisition may be axial, sagittal, or coronal). The smaller of these measures is the short axis. For example, an abdominal node that is reported as being 20 mm (30 mm has a short

axis of 20 mm and qualifies as a malignant, measurable node. In this example, 20 mm should be recorded as the node measurement. All other pathological nodes (those with short axis  $\geq$  10 mm but  $<$  15 mm) should be considered non-target lesions. Nodes that have a short axis of  $<$  10 mm are considered non-pathological and should not be recorded or followed.

All lesions (or sites of disease) not selected as target lesions (measurable or non-measurable), including pathological lymph nodes, should be identified as non-target lesions and should also be recorded at baseline. Measurements are not required. It is possible to record multiple non-target lesions involving the same organ as a single item on the Case Report Form (CRF) (e.g., "multiple enlarged pelvic lymph nodes" or "multiple liver metastases").

## **CALCULATION OF SUM OF DIAMETERS**

A sum of the diameters (longest diameter for non-lymph node lesions, short axis for lymph node lesions) will be calculated for all target lesions at baseline and at each subsequent tumour assessment as a measure of tumour burden.

### Measuring Lymph Nodes

Lymph nodes identified as target lesions should always have the actual short axis measurement recorded (measured in the same anatomical plane as the baseline examination), even if the node regresses to  $<$  10 mm during the study. Thus, when lymph nodes are included as target lesions, the sum of diameters may not be zero even if complete response criteria are met, since a normal lymph node is defined as having a short axis of  $<$  10 mm.

### Measuring Lesions That Become Too Small to Measure

During the study, all target lesions (lymph node and non-lymph node) recorded at baseline should have their actual measurements recorded at each subsequent evaluation, even when very small (e.g., 2 mm). However, sometimes lesions or lymph nodes that are recorded as target lesions at baseline become so faint on CT scan that the radiologist may not feel comfortable assigning an exact measurement and may report them as being too small to measure. When this occurs, it is important that a value be recorded on the CRF, as follows:

- If it is the opinion of the radiologist that the lesion has likely disappeared, the measurement should be recorded as 0 mm.
- If the lesion is believed to be present and is faintly seen but too small to measure, a default value of 5 mm should be assigned and "too small to measure" should be ticked. (Note: It is less likely that this rule will be used for lymph nodes since they usually have a definable size when normal and are frequently surrounded by fat such as in the retroperitoneum; however, if a lymph node is believed to be present and is faintly seen but too small to measure, a default value of 5 mm should be assigned in this circumstance as well and "too small to measure" should also be ticked).

To reiterate, however, if the radiologist is able to provide an actual measurement, that should be recorded, even if it is + 5 mm, and in that case "too small to measure" should not be ticked.

